4 STUDY OBJECTIVES

4.1 Primary Objective

The primary objective is to assess the cumulative anti-rotavirus serum IgA response (defined as a \geq 3 fold increase from baseline) 4 weeks after 3 doses of RV3-BB administered in a neonatal schedule at a vaccine titre of 1x10⁷, 3 x 10⁶ or 1 x 10⁶.

4.2 Secondary Objectives

The secondary objectives of the study are;

- To assess the cumulative anti-rotavirus serum IgA response (defined as a ≥3 fold increase from baseline) 4 weeks after 3 doses of RV3-BB administered in an infant schedule at a vaccine titre of 1 x 10⁷.
- To assess cumulative vaccine take and components of vaccine take after 3 doses of RV3-BB (titre of 1 x 10⁷) administered in a neonatal schedule versus three doses of RV3-BB in an infant schedule at a vaccine titre of 1 x 10⁷.
- To assess cumulative vaccine take and the components of RV3-BB vaccine take after 3 doses of RV3-BB administered as a neonatal schedule at a vaccine titre of 1 x 10⁷, 3 x 10⁶ or 1 x 10⁶.

To assess cumulative vaccine take and the components of vaccine take after 2 doses of RV3-BB administered as a neonatal schedule at a vaccine titre of 1×10^7 , 3×10^6 or 1×10^6 or 2 doses in the infant schedule at a vaccine titre of 1×10^7 .

- To assess cumulative vaccine take and components of vaccine take after the first dose of RV3-BB administered as a neonatal schedule at a vaccine titre of 1 x 10⁷, 3 x 10⁶ or 1 x 10⁶ compared to placebo (1st dose of IP in the infant schedule).
- To assess cumulative vaccine take and components of vaccine take after the first dose of RV3-BB at a vaccine titre of 1 x 10⁷, 3 x 10⁶ or 1 x 10⁶ in the neonatal schedule compared with the first dose of RV3-BB at a vaccine titre of 1 x 10⁷ in the infant schedule.
- To describe the geometric mean titre of the anti-rotavirus serum IgA response after 3 doses of RV3-BB administered as a neonatal or an infant schedule
- To describe the safety and tolerability of RV3-BB when administered as an infant or as a neonatal schedule.
- To describe the occurrence of diarrhea episodes in participants, according to severity and detection of wild-type rotavirus.

4.3 Exploratory Objectives

The basis of the exploratory objectives is to further understand potential barriers to rotavirus vaccine efficacy in the region. The exploratory objectives are;

- To describe Histo-blood Group Antigens (Lewis and secretor) status of participants in association with anti-rotavirus sero-conversion and cumulative vaccine take after 3 doses RV3-BB administered in either the neonatal schedule (any titre) or infant schedule.
- To assess maternal anti-rotavirus IgA and IgG levels in association with anti-rotavirus IgA seroconversion and cumulative vaccine take in participants following receipt of RV3-BB administered in either the neonatal schedule (at any vaccine titre) or infant schedule at a vaccine titre of 1 x 10⁷.
- To describe the gut microbiome in participants receiving RV3-BB administered in the neonatal schedule (at any vaccine titre) or infant schedule at a vaccine titre of 1×10^7 .
- To describe innate and adaptive immune responses in infants vaccinated with RV3-BB administered in a neonatal vaccine schedule (any titre) or in the infant schedule at a vaccine titre of 1×10^7 .

5 TRIAL PLAN

5.1 Study Design

This is a Phase II, randomised, double-blind, placebo-controlled, four-arm parallel group study of two different dosing schedules of oral RV3-BB, and placebo.

Approximately 688 participants will be randomised to the study; 172 to each treatment arm.

Pregnant women will be invited to provide preliminary consent for the study prior to labour and delivery. A maternal blood sample and a stool sample will be collected. Following delivery, those who remain interested will be invited to provide written informed consent for their baby to participate in the study.

Following confirmation of eligibility for the trial post-birth, participants will be randomised in a 1:1:1:1 ratio to one of four treatment arms; high-dose, mid-dose or low-dose neonatal schedule, or a high-dose infant schedule. Each study participant will receive four oral doses of IP, with each administration consisting of 1 mL RV3-BB Rotavirus Vaccine or 1mL of placebo. All participants will receive a total of 3 doses of RV3-BB vaccine, one dose of placebo, and one dose of Rotarix®.

A baseline stool sample will be collected prior to the administration of the first dose of IP. A stool sample will also be collected on either Day 3, 4 or 5 following each dose of IP. Samples will also be collected for any cases of diarrhoea (defined as 3 or more stools that are looser than normal for that participant).

[figure not shown]
A saliva sample will be collected at birth and prior to IP doses 2, 3 and 4.

Cord blood will be collected at birth, and blood samples taken prior to IP doses 1 (if cord blood not collected) 2, 3 and 4, and prior to the Rotarix® dose.

Participants will be followed until 18 weeks of age. Face to face visits will be conducted at least monthly. Adverse events, including blood-in-stool occurrences, and diarrhoea episodes will be recorded for the duration of the study.

The recruitment period is estimated at 9 months. The study period for each participant will be 18 weeks, and the total duration of the study approximately 15 months.

An independent Data Safety Monitoring Board (DSMB) will review safety data at agreed recruitment and progression milestones throughout the study, as agreed and documented in the DSMB Charter. The DSMB will recommend whether the study continues unchanged, continues with amendments, or is stopped. Recruitment will continue during the DSMB review periods.

5.2 Study Population

5.2.1 Number of Participants and Study Sites

Approximately 688 babies will be randomised across approximately four sites in Malawi. Study visits will be conducted at the sites or at participant homes.

5.2.2 Trial Selection Record

Investigators must keep a record of those who were considered for the study but were not enrolled. This information is necessary to establish that the patient population was selected without bias.

Only babies who meet all of the inclusion and none of the exclusion criteria will be eligible to participate in the study. No protocol waivers for eligibility will be allowed.

5.2.3 Inclusion Criteria

- Neonate is less than 6 days (≤ 144 hours) of age at the time of first dose.
- Neonate is in good health as determined by clinical judgment, including a medical history and physical exam, which confirms the absence of a current or past disease state considered significant by the investigator.
- Neonate birth weight 2500-4000g inclusive or 2250-4000g inclusive at Visit 1.
- Neonate's parents/guardians expect to be available for the duration of the study, and agree to adhere to all protocol requirements.
- Neonate's parents/guardians have provided written informed consent prior to study-related procedures being performed.

5.2.4 Exclusion Criteria

- Any medical, psychiatric, or social condition of a parent/guardian that in the opinion of the investigator would prevent the neonate's parents/guardians from giving proper informed consent or from complying with the study protocol.
- Neonates with known or suspected major congenital malformations or genetically determined disease.
- Neonates with intussusception.
- Neonates with a known or suspected bleeding diathesis, or any condition that may be associated with a prolonged bleeding time.
- Neonates who have ever received any blood products, including immunoglobulin, or for whom receipt of any blood product during the course of the study is anticipated.
- Neonates in whom EPI vaccines or components are contraindicated.
- Neonates who have received or who expect to receive during the study period, any rotavirus vaccine other than those which will be administered as part of this study.
- Neonates who have ever received, or who are anticipated to receive during the study period, any investigational agent other than those which will be administered as part of this study.

- Neonates with a previous anaphylactic reaction to any drug, vaccine or vaccine component.
- Neonates with a significant evolving neurological disorder.
- Neonates whose parents/guardians are site team employees with direct involvement with the investigators, or who are working on the study.
- Neonates who have been exposed to immunosuppressive courses of glucocorticosteroids, cytotoxic drugs or blood products through prenatal exposure and/or breast milk in the four weeks prior to randomisation should be discussed with the Medical Monitor and sponsor and a decision on eligibility made on a case by case basis.
- Neonates with diarrhoea or vomiting in the 24 hours preceding randomisation.
- Neonates with any moderate or severe illness, and/or who have a temperature of ≥37.5°C axillary/oral or ≥38°C rectal/tympanic within the 48 hours preceding randomisation.

5.3 Screening failures

A screening failure is a participant for whom informed consent is obtained and documented in writing from the legally authorised representative, but who is deemed ineligible for the trial and is therefore not randomised. Reasons for screening failure include conditions detected on history or during the screening examination that deem the participant ineligible.

Records will be kept of screening failures, including reasons.

5.4 Concomitant medications and vaccines

The following medications are contraindicated for use at any time during the study period:

- Immunosuppressive therapy, including immunosuppressive courses of systemic corticosteroids
- Immunoglobulins (antibodies) or other blood products;
- Other investigational products
- Other rotavirus vaccines;
- Aspirin or aspirin-containing medications
- Medications that may affect the liver, for example, chloramphenicol including eye drops. A list of other drugs will be provided in the Study Reference Manual (SRM).

If a contraindicated medication is administered, future IP dosing of the participant will be decided by MCRI (or designee) on a case-by-case basis.

All participants will receive EPI vaccines during the study at scheduled time points. Standard vaccines approved for use in Malawi will be administered by study staff during the study but will be provided via usual channels, not provided by the study. The exceptions are polio vaccine, which will be provided by the study as IPV rather than the usual OPV, and Rotarix® which will only be administered at Visit 9.

6 TRIAL PROCEDURES

Table 1: Schedule of Procedures

Visit	Pre-study	1	2	3	4	5	6	7	8	9 ⁹
Timing	Second	Day 1	Day 8	Week 6	Week 7	Week 10	Week 11	Week 14	Week 15	Week 18
Window	Second trimester to birth	Birth to 144 hrs old	7±1 days post V1	+7 days	7±1 days post V3	±7 days and at least 21 days post V3	7±1 days post V5	±7 days and at least 21 days post V5	7±1 days post V7	±7 days and at least 21 days post V7
Preliminary consent	Х									
Cord blood collection	Х									
Maternal blood sample	Х									
Maternal stool sample	Х									
Study consent		Х								
Eligibility confirmation		Х								
Demographics and medical history		х								
Physical exam		Х								
Vital signs ¹		Х	Х	Х	Х	Х	Х	Х	Х	Х
Stool sample	X ⁵	X 6		X ⁶		X6		X ⁶		
Saliva sample		Х		Х		Х		Х		
Randomisation		Х								
IP administration		Х		Х		Х		Х		
Antacid administration ²				Х		Х		Х		
EPI vaccine administration ⁹		Х		Х		Х		Х		Х
IPV administration				Х		Х		Х		
Rotarix® administration										X ⁷
Pre dose blood sample		X ¹⁰		Х		Х		Х		Х
Issue/review diarrhoea log ³		Х		Х		Х		Х		Х
Issue/review study reminder Card ³		Х		Х		х		х		х
Issue stool sample kits ³		Х		Х		Х		Х		
Feeding review ⁴		Х	Х	Х	Х	Х	Х	Х	Х	Х
AE recording		Х	Х	Х	Х	Х	Х	Х	Х	Х

Con med recording	Х	Х	Х	Х	Х	Х	Х	Х	Х
Follow up contacts		Weekly contact (clinic, home or telephone) throughout the study							

1. Temperature, pulse rate, respiratory rate. At dosing visits vital signs will be measured within one hour pre dose and 15 and 30 mins post dose.

2. 2mL of Mylanta Original® will be administered within the 10 minutes prior to the IP dose.

3. Logs, reminder card and kits will be issued and reviewed as required.

4. Record if baby receiving breast milk, formula, or other.

5. A pre dose stool sample will be collected at any time from birth before the first dose of IP.

6. A stool sample will be collected 3 - 5 days post IP dose.

7. If the participant withdraws prior to receiving all IP doses they will be given a Rotarix® dose one month following their last dose of IP.

8. Day 1 pre dose sample will be cord blood.

9. EPI vaccines will be provided via usual supplier (not study) but may be administered by study staff at appropriate time points according to standard schedule. The exceptions are OPV and other rotavirus vaccines, which will not be given (see Section 5.4).

10. A 1.0mL blood sample will be collected if cord blood is not able to be collected.

6.1 Recruitment

Sites will have information about the study on display and pregnant women will be identified at the time of antenatal care. During the second or third trimester, pregnant women will be approached by a member of the study team who will describe the study to them, provide written information and, if they are interested, arrange to discuss the study in more detail at a later time. Expectant women will be encouraged to discuss the study with their partner, usual doctor, midwife, and family members.

6.1.1 Informed Consent

The investigator or delegate must obtain the written informed consent according to local laws and requirements before any study-related procedures are performed, including any study specific screening procedures.

A two-stage consent process will be followed:

- Pregnant women who are interested in participating will be invited to provide preliminary consent during the second or third trimester and prior to going into labour. This consent is to allow a pre-birth maternal blood sample (taken any time from consent until Visit 1), collection of cord blood at the birth, and collection of their baby's stool (taken from birth up to Visit 1). Consent for a stool sample from the pregnant woman will also be requested.
- Post birth, the parents/guardians will be invited to provide consent for their baby to participate in the study.

6.2 Birth Procedures

An approximate 2.5 mL cord blood sample will be taken immediately following delivery, after the umbilical cord has been cut. A baseline stool sample will also be collected from the baby. Inability to collect a baseline stool sample does not exclude the baby from further trial participation.

If not previously obtained, a maternal blood sample (approximately 1mL) will also be collected. Inability to collect a maternal blood sample does not exclude the baby from further trial participation.

If not previously obtained, a maternal stool sample will also be collected. Inability to collect a maternal stool sample does not exclude the baby from further trial participation

6.3 Visit 1 Procedures (0-5 days of age)

After consent for the baby to participate in the study is obtained, the following will be conducted/recorded at any time up to and including 5 days (144 hours) of age;

- Demographic data including date of birth, gender, ethnicity, gestational age and birth weight, current weight and height/length.
- Medical history.
- Feeding status (breast milk and/or formula).

- All medications, supplements, traditional/complementary/herbal products and immunisations administered to the baby since birth.
- All medications, supplements, traditional/complementary/herbal products and immunisations administered to the mother from 4 weeks pre-delivery.
- Physical examination (see section 8.1).
- Vital signs (see section 8.3).
- Collection of a pre dose stool sample from the baby (inability to collect a stool sample does not exclude the baby from further trial participation).
- Collection of a saliva sample from the baby.
- Collection of a 1.0mL pre dose blood sample from the baby (when cord blood is not collected)

Confirmation of eligibility must be completed within the 24 hours prior to administration of the first dose of IP. If the administration of the dose is delayed, assessments must be repeated.

Eligible participants will be randomised and the following procedures performed pre dose;

• Vital signs (see section 8.3) within the 60 minutes pre dose.

IP will be administered. A dose of 1 ml will be given orally from a syringe (see section 10.9).

The following procedures will be performed post dose;

- Administer any scheduled EPI vaccines other than OPV and rotavirus vaccines according to local guidelines (see section 9.2).
- Vital signs (see section 8.3) will be measured at 15 minutes and 30 minutes post dose (±5 minutes).
- Record any AE.
- Issue the parents/guardians with the Study reminder card and provide instructions for its completion (see section 8.3).
- Issue the parents/guardians with the Diarrhoea Log and provide instructions for its completion (see section 8.4) and for notifying the site of any episodes of diarrhoea.
- Issue kits and containers for stool and diarrhoea samples, and instructions for collection and storage of samples (see section 8.4).
- Explain the definition of diarrhoea (three or more stools in a 24 hour period that are looser than normal for that child).
- Issue thermometer and instructions for measuring temperature (see section 8.3) and for notifying the study staff if the participant develops a temperature $\geq 37.5^{\circ}$ C.
- Remind the parents/guardians of potential AEs and to contact the study staff immediately if any illness or hospitalisation occurs during the study period.

Study staff will contact the parents/guardians (clinic or home visit) the day following dosing, and on day 3, 4 or 5 following dosing, to review AEs and medications, and collect stool and diarrhoea samples.

6.4 Visit 2 (7 ±1 days after Visit 1)

The following will be performed/recorded:

- Vital signs (see section 8.3).
- Review AEs.
- Review concomitant medications (participant, and mother if breastfeeding).
- Review feeding status.
- Review Diarrhoea Log and study reminder card.

Throughout the remainder of the study, study staff will contact the parents/guardians at least weekly via telephone, home visit, or clinic visit, to review AEs, medications, and diarrhoea episodes. If the baby has a diarrhoea episode a sample will be collected.

6.5 Visit 3 (Week 6 +7 days)

The following will be performed/recorded at the trial site no earlier than 6 weeks of age:

- Review AEs.
- Review concomitant medication.
- Review feeding status.
- Review Diarrhoea Log and study reminder card.
- Collect a pre dose blood sample.
- Collect a saliva sample.
- Vital signs (see section 8.3) within the 60 minutes pre dose.
- Administer 2mL of Mylanta Original® antacid formulation within the 10 minutes pre dose.
- Administer the IP dose.

The following procedures will be performed post dose;

- Administer IPV and any scheduled EPI vaccines other than OPV and rotavirus vaccines according to local guidelines (see section 9.2).
- Vital signs (see section 8.3) will be measured at 15 minutes and 30 minutes post dose (±5 minutes).
- Record any AEs.
- Issue kits and containers for stool and diarrhoea samples, and instructions for collection and storage of samples (see section 8.4).

Study staff will contact the parents/guardians (clinic or home visit) the day following dosing, and once on day 3, 4 or 5 following dosing, to review AEs and medications, and collect stool and diarrhoea samples.

6.6 Visit 4 Procedure (7 ±1 days after Visit 3)

The following will be performed/recorded:

- Vital signs (see section 8.3).
- Review AEs.
- Review concomitant medications (participant, and mother if breastfeeding).

• Review feeding status.

6.7 Visit 5 (Week 10 ±7 days)

The following will be performed/recorded at the trial site, no sooner than 21 days after the previous dose of IP (Visit 3):

- Review AEs.
- Review concomitant medication.
- Review feeding status.
- Review Diarrhoea Log and study reminder card.
- Collect a pre dose blood sample.
- Collect a saliva sample.
- Vital signs (see section 8.3) within the 60 minutes pre dose.
- Administer 2mL of Mylanta Original® antacid formulation within the 10 minutes pre dose.
- Administer the IP dose.

The following procedures will be performed post dose;

- Administer IPV and any scheduled EPI vaccines other than OPV and rotavirus vaccines according to local guidelines (see section 9.2).
- Vital signs (see section 8.3) will be measured at 15 minutes and 30 minutes post dose (±5 minutes).
- Record any AEs.
- Issue kits and containers for stool and diarrhoea samples, and instructions for collection and storage of samples (see section 8.4).

Study staff will contact the parents/guardians (clinic or home visit) the day following dosing, and once on day 3, 4 or 5 following dosing, to review AEs and medications, and collect stool and diarrhoea samples.

6.8 Visit 6 (7 ±1 days after Visit 5)

The following will be performed/recorded:

- Vital signs (see section 8.3).
- Review AEs.
- Review concomitant medications (participant, and mother if breastfeeding).
- Review feeding status.

6.9 Visit 7 (Week 14 ±7 days)

The following will be performed/recorded at the trial site, no sooner than 21 days after the previous dose of IP (Visit 5):

- Review AEs.
- Review concomitant medication.
- Review feeding status.

- Review Diarrhoea Log and study reminder card.
- Collect a pre dose blood sample
- Collect a saliva sample
- Vital signs (see section 8.3) within the 60 minutes pre dose.
- Administer 2mL of Mylanta Original® antacid formulation within the 10 minutes pre dose.
- Administer the IP dose.

The following procedures will be performed post dose;

- Administer IPV and any scheduled EPI vaccines other than OPV and rotavirus vaccines according to local guidelines (see section 9.2).
- Vital signs (see section 8.3) will be measured at 15 minutes and 30 minutes post dose (±5 minutes).
- Record any AE.
- Issue kits and containers for stool and diarrhoea samples, and instructions for collection and storage of samples (see section 8.4).

Study staff will contact the parents/guardians (clinic or home visit) the day following dosing, and once on day 3, 4 or 5 following dosing, to review AEs and medications, and collect stool and diarrhoea samples.

6.10 Visit 8 (7 ±1 days after Visit 7)

The following will be performed/recorded:

- Vital signs (see section 8.3).
- Review AEs.
- Review concomitant medications (participant, and mother if breastfeeding).
- Review feeding status.

6.11 Visit 9 (Week 18 ±7 days)

The following will be performed/recorded at the trial site, no sooner than 21 days after the previous dose of IP (Visit 7):

- Review AEs.
- Review concomitant medication.
- Review feeding status.
- Review Diarrhoea Log.
- Collect a pre dose blood sample.
- Vital signs (see section 8.3) within the 60 minutes pre dose.
- Administer Rotarix®.
- Administer any scheduled EPI vaccines according to local guidelines (see section 9.2).

Study staff will contact the parents/guardians (clinic or home visit) the day following dosing.

6.12 Discontinuation of Participants

6.12.1 Criteria for discontinuation

The participant may be discontinued from the trial at any time at the discretion of the investigator(s).

Specific reasons for withholding further doses or discontinuing a participant in this trial may include:

- Withdrawal of informed consent by parents/guardians.
- Participant lost to follow-up.
- Protocol non-compliance.
- Investigator considers that it is not in the interest of the participant to continue.
- MCRI terminates the study for administrative, financial or other reasons.

If a participant is discontinued from dosing, unless they withdraw consent they should continue to have blood samples collected at the scheduled time points and continue to collect diarrhoea samples and complete the Diarrhoea Log. Investigators are encouraged to discuss possible treatment discontinuations and withdrawals with the Medical Monitor, if appropriate, prior to ceasing treatment or withdrawing the infant. The decision to replace withdrawn subjects will be made on a case by case basis. Participants withdrawn due to AEs will not be replaced.

All withdrawn participants should be seen and assessed approximately 28 days after their last dose of IP, primarily for the purposes of monitoring participant safety. Wherever possible, AEs should be followed up until resolution. Parents/guardians who withdraw consent should be asked whether they agree to this follow up.

Participants who withdraw from study or IP will continue to receive IPV until the course is complete. They will receive Rotarix® at standard scheduled time points according to the National Immunisation Program.

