Because the risk of intussusception is highest following the first dose of a rotavirus vaccine and is highest if the first dose is delivered late, the WHO SAGE meeting initially recommended that the first dose of a rotavirus vaccine be restricted to < 6 months of age to limit the risk of intussusception. This provided a major challenge for the implementation of rotavirus vaccines in developing countries where timely administration of the current Expanded Program on Immunisation vaccines is often not achieved and the exact age of infants may be unknown (Buttery & Graham, 2009). However, there are concerns that restrictions on the age of administration of the first and last dose of rotavirus vaccines has prevented vaccination of many vulnerable children in settings where the DTP doses are given late. In response to this concern the WHO have now relaxed age restrictions for rotavirus vaccination by allowing infants to receive rotavirus vaccines together with DTP regardless of the time of vaccination as long as this is after 6 weeks of age (WHO, 2013).

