3.6.1 Advantages of the birth dose strategy

Rotavirus infection often occurs very early in life, particularly in developing countries. In Africa, 38% of hospitalisation due to rotavirus infection occurs in infants less than 6 months of age (Cunliffe, 1998). The rotavirus seropositivity rate among placebo recipients 1 month after the last dose had been given in a trial of Rotarix® was greater among Malawian infants than among South African infants (40.4% vs 16.7%) suggesting that Malawian infants have high exposure to wild-type rotavirus infection in the first 5 months of life (Cunliffe et al., 2012). The current vaccines administered from 6 weeks of age, with completion of a 2- or 3-dose course at 4–6 months may be too late to protect some infants. Neonatal vaccine administration offers the earliest possible protection.

Providing a rotavirus vaccine at birth has the potential to address sub-optimal efficacy of rotavirus vaccination in high burden countries and improve safety concerns. It also may increase the proportion of infants living in remote regions completing a full course of a rotavirus vaccine.

Birth dose administration may limit interference to vaccine take, as most newborns have a neutral gastric environment and minimal breast milk intake. The intestinal microbiota is not yet well established and intussusception is rare (Dennehy et al., 2007). Based on the unique structural and functional characteristics of neonatal rotavirus strains, it is proposed that RV3-BB is an ideal vaccine for a birth dose strategy. Natural infection with RV3 is associated with replication without symptoms but provides heterotypic protection against severe rotavirus disease for the first 3 years of life (Bishop et al., 1983). A birth dose of a rotavirus vaccine may also be safer as the natural intussusception risk is lowest in the neonatal period.

Neonatal rotavirus strains replicate well in the immature newborn intestine despite the presence of maternal and breast milk antibodies. They generally cause asymptomatic infections, but induce a protective immune response against rotavirus on re-infection (Bishop et al., 1983). The RV3-BB rotavirus vaccine based on a neonatal rotavirus strain may be the ideal candidate for a birth dose vaccine strategy.

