9.2 Routine Concurrent Vaccines

During the study period, all trial participants should continue to receive standard EPI immunisations in accordance with the routine schedule and local recommendations, with the following exceptions;

- All study participants will be administered IPV by study staff at weeks 6, 10 and 14, rather than OPV, as a transition from OPV to IPV in Malawi is planned during the period of the trial
- Participants will not receive the standard Rotarix® schedule of vaccines during the study. As RV3-BB vaccine efficacy is not yet established, all participants will be administered a single dose of Rotarix® approximately one month after their final dose of IP.

Additional licensed vaccines may be administered as appropriate for the participant.

Commercial name, batch number, and date of administration will be recorded for all vaccinations.

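### Two rules for when infants who stop IP early receive Rotarix conflict, and one allows a dose before 6 weeks of age; the supportive ITT Kaplan-Meier analysis has no clear rule for IgA drawn afterwards

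*Protocol*

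**What the plan says.** **Timing of Rotarix after an early stop.** Footnote 7 to Protocol Table 1, repeated as footnote 7 in SAP 4.1.3, covers a participant who withdraws before all IP doses. It gives a Rotarix "dose one month following their last dose of IP". Protocol 6.12.1, repeated in SAP 10.1.1, covers participants who withdraw from the study or from IP. It gives them Rotarix "at standard scheduled time points according to the National Immunisation Program". No text says which rule prevails.

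**Minimum age.** Protocol 3.5.1 reports the WHO position that rotavirus vaccine may accompany DTP at any time, "as long as this is after 6 weeks of age". Protocol 3.6.1 speaks of "The current vaccines administered from 6 weeks of age". Neither version of footnote 7 carries an age floor. The first IP dose is given at up to 144 hours of age (Protocol 5.2.3).

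**Blood samples and analysis.** Protocol 6.12.1 says of infants who stop dosing without withdrawing consent that "they should continue to have blood samples collected at the scheduled time points". The ITT set (SAP 6.1.3) needs at least one IP dose and evaluable baseline and post-baseline blood; Rotarix is not mentioned. SAP 7.1.4 and 9.1.2 estimate cumulative IgA response up to 18 weeks of age by Kaplan-Meier, with a 20% non-inferiority rule. SAP 9.1.1 ties a responder to IP doses 1–3 in the neonatal arms and 2–4 in the infant arm.

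**The concern.** The two rules apply to the same infants and give different ages and possibly different numbers of doses: a single dose in footnote 7, plural time points in 6.12.1. Sites working from the schedule table and sites working from the discontinuation section would treat early stoppers differently. Taken literally for an infant who stops after the birth dose, footnote 7 directs a licensed live vaccine at an age below the minimum the protocol itself cites.

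The analysis question follows from the dosing question. Under either rule, an infant still being bled can have serum drawn after Rotarix. A threefold IgA rise in that sample may be due to Rotarix rather than RV3-BB. SAP 9.1.8 handles the same attribution problem for stool by counting only vaccine-like sequences; serum IgA has no counterpart. With similar stopping across arms and a lower response among lower-titre stoppers, counting such rises narrows the difference between titres. That favours non-inferiority.

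**Working it through.** **1. The two rules side by side**

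| Place | Who | Rotarix timing |
|---|---|---|
| Protocol Table 1 fn 7; SAP 4.1.3 fn 7 | withdraws before all IP doses | one dose, one month after last IP |
| Protocol 6.12.1; SAP 10.1.1 | withdraws from study or IP | national programme time points |

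The second row covers withdrawal from the study and from IP alike, so reading footnote 7 as study withdrawal only does not separate the groups.

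**2. Age at Rotarix under footnote 7**

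Age = age at last IP dose + one month, taken as 28–31 days. Dose windows are from Protocol Table 1.

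- Stop after dose 1: 0 + 28 = 28 to 6 + 31 = 37 days (4.0–5.3 weeks). Always below 42 days.
- Stop after dose 2: 42 + 28 = 70 to 49 + 31 = 80 days (10.0–11.4 weeks).
- Stop after dose 3: 63 + 28 = 91 to 77 + 31 = 108 days (13.0–15.4 weeks).

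Only a stop after dose 1 gives a dose before 6 weeks.

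**3. Which bleeds follow Rotarix**

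- Loose reading (any sample up to 18 weeks counts), footnote 7: after a stop at dose 1, weeks 6, 10, 14 and 18; after a stop at dose 2, weeks 14 and 18.
- Loose reading, national programme rule, assuming a first dose at 6 weeks after that visit's bleed: weeks 10, 14 and 18 for a dose-1 stop.
- Strict reading (SAP 9.1.1 limits response to RV3-BB doses): for a dose-1 stop under footnote 7 only week 6 remains. It falls 42 − 37 = 5 to 49 − 28 = 21 days after Rotarix.

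**4. Size of the effect on the ITT comparison**

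The plan has no figure of its own here to reproduce. From it I take the 20-point margin, 50% control response, one-sided 0.025 level and 172 per arm, the largest possible ITT size. Assumed, because the documents give none of them:

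- f, the share of each arm that stops, receives Rotarix and is bled afterwards;
- r, the share of their non-responders who then convert;
- sH and sL, the response among stoppers before Rotarix in the high and lower titre arms.

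At the non-inferiority boundary (true 50% against 30%):

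- observed pH = 0.50 + f·r·(1 − sH)
- observed pL = 0.30 + f·r·(1 − sL)
- observed gap = 0.20 − f·r·(sH − sL)

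Example: f = 0.05, r = 0.5, sH = 0.25, sL = 0.15. pH = 0.50 + 0.025 × 0.75 = 0.51875; pL = 0.30 + 0.025 × 0.85 = 0.32125; gap = 0.1975.

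The error is the exact binomial probability that the one-sided 0.025 score test (restricted maximum likelihood variance, margin 0.20) declares non-inferiority. This test stands in for the Kaplan-Meier interval. With f = 0 the error is 2.52%. Cells show r = 0.3 then r = 0.5, on the loose reading.

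| Stoppers' response, high / lower | f = 2% | f = 5% | f = 15% |
|---|---|---|---|
| 10% / 6% | 2.52%, 2.52% | 2.53%, 2.55% | 2.64%, 2.82% |
| 25% / 15% | 2.57%, 2.60% | 2.64%, 2.73% | 2.97%, 3.41% |
| 50% / 30% | 2.64%, 2.73% | 2.83%, 3.07% | 3.60%, 4.61% |

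Of 172 infants, f = 2%, 5% and 15% are 3.4, 8.6 and 25.8.

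Unequal stopping moves the error either way. With stoppers at 25% / 15%, 10% affected in the high arm and 5% in the lower arm gives 1.55%, 1.11%. The reverse gives 4.50%, 6.46%. Blinding gives no reason to expect this.

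**The case against.** The strongest reply is that this is one footnote out of step with the section dedicated to discontinuation, and that the definitions already contain most of the analysis gap. Much of that stands.

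- **Sections 5.4 and 9.2.** A reader might count these as third and fourth conflicting rules. Section 5.4 says of Rotarix, "which will only be administered at Visit 9"; section 9.2 gives it "approximately one month after their final dose of IP". Both can be read as the default for infants on schedule. The synopsis uses the final dose to mean dose 4 at about 14 weeks, which leads to the usual week-18 Rotarix. They need a cross-reference at most.
- **The 28-day visit.** Protocol 6.12.1 says "All withdrawn participants should be seen and assessed approximately 28 days after their last dose of IP". A reader might infer that this is when an early Rotarix dose would be given. The section gives safety monitoring as the main purpose and does not link Rotarix to that visit.
- **Harm.** A reader might infer a shown safety risk from a dose before 6 weeks. The documents do not show one, and three arms receive live RV3-BB at 0–5 days by design. The point is that a stated rule breaches an age minimum the protocol cites.
- **Samples at weeks 6 to 18.** A reader might treat all of these as contaminated. SAP 9.1.1, and Protocol 7, where the endpoint runs to 4 weeks after three RV3-BB doses, can be read as limiting response to samples following RV3-BB. On that reading most later samples drop out. Neither place says so for an infant who has since had Rotarix, and the Kaplan-Meier text sets its horizon by age, so the question stays open.
- **Relevance.** The ITT analysis is supportive. The per-protocol set requires all three RV3-BB doses, completers are bled before Rotarix at Visit 9, and the Newcombe and GEE comparisons are defined after dose 3. All of this is correct.

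**Conclusion.** The dosing conflict is established from the text alone. Footnote 7 in both documents and Protocol 6.12.1 with SAP 10.1.1 give different Rotarix timing for the same infants. For a stop after the birth dose, footnote 7 gives 28–37 days of age against a cited minimum of 42. How many infants this would touch is not stated.

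The analysis gap is secondary. The supportive ITT Kaplan-Meier result carries its own 20% rule and does not clearly exclude IgA drawn after Rotarix. With similar stopping across arms, one-sided error moves from 2.5% to about 2.5–3.1% when 2–5% of each arm is affected. That rests wholly on assumed f, r and stopper response, and on the loose reading of which samples count. A reader might take the 4.6% figure as the risk; it needs 15% affected, 50% conversion and the full 20-point gap among stoppers, none of which the documents support. Nor do they support a threat to the primary conclusion, since the primary per-protocol analysis is largely unaffected.

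Both points should be corrected, mainly for the dosing conflict.

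**What to change.** **Dosing.** Replace footnote 7 in Protocol Table 1 and SAP 4.1.3, and use the same sentence in Protocol 6.12.1 and SAP 10.1.1:

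> Infants who stop IP early receive Rotarix at national programme time points, with the first dose not before 6 weeks of age, and after any study blood draw due at that visit.

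This leaves the number of doses to the national programme. A one-month rule with a 6-week floor would also remove the conflict, but it would change the plural time points to one timed dose, which needs its own clinical argument. Add a cross-reference in Protocol 5.4 and 9.2 if wanted.

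**Analysis.** Add to SAP 9.1.2, for the ITT Kaplan-Meier analysis:

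> IgA drawn after any Rotarix dose is not counted as an RV3-BB response; the infant is censored at the last sample before that dose.

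Show the all-samples result as a sensitivity analysis, because censoring at Rotarix may be informative.

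**Cost.** Four wording edits, up to two cross-references and one SAP sentence. A few ITT samples go unused in the main Kaplan-Meier result. No new data are needed, since Protocol 9.2 already records vaccination dates. SAP section 5 shows that laboratory testing had begun. If dosing is over, the protocol edits come too late to change practice, but the SAP sentence can still be set before database lock and the age at Rotarix listed for early stoppers.
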